##### **Home PEF (morning and evening)**

Change from baseline in morning and evening PEF at Week 52 will each be summarized and analyzed using a similar model as the model for change from baseline in pre dose/pre-BD FEV1, as described in Section 8.5.7.1

##### **European quality of life-5 dimensions-5 levels (EQ-5D-5L)**

The EQ-5D-5L responses from each dimension and the visual analogue scale (VAS) will be summarized by treatment group and period. Shift tables will be produced for each dimension, and the change from baseline in VAS will be summarized with descriptive statistics by visit.

### **8.5.8 Safety and tolerability**

All safety variables will be summarized using the safety analysis set and biomarker positive and negative populations, and data presented according to treatment received.

#### **8.5.8.1 Adverse events**

AEs will be summarized separately for the treatment and follow-up periods, as defined in Section 6.3. AEs occurring during the run-in period, or occurring post-treatment (as per the definition above) will be listed, but not summarized.

An overall summary table will be produced showing the number and percentage of subjects with at least 1 AE in any of the following categories; AEs, SAEs, deaths due to AE, DAEs, and other significant adverse events (OAEs). The total number of AEs in the different AE categories in terms of AE counts will also be presented (i.e., accounting for multiple occurrences of the same event in a subject).

AEs will be summarized by SOC and PT assigned to the event using MedDRA. For each PT, the number and percentage of subjects reporting at least one occurrence will be presented i.e., for a subject multiple occurrences of an AE will only be counted once.

AEs (by PT) will be summarized by causality and maximum intensity. If a subject reports multiple occurrences of the same AE, the maximum intensity will be taken as the highest recorded maximum intensity (the order being mild, moderate, and severe). SAEs, OAEs, DAEs, and deaths will also be summarized in separate tables.

The rate of AEs per person-years at risk, calculated as (number of subjects reporting AE)/(total time at risk of AE), will also be reported. Rates will typically be expressed in terms of events per 100 subject-years.

Separate listings of subjects with AEs, SAEs, death due to AE, or discontinuations due to AEs will be presented.

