However, because it is believed that the Th2 response may be of importance in the defense against helminthic parasitic infections, a theoretical risk for such infestations exists. IL-13 may also play a role in regulating tumours (Hallett et al 2012), and although evidence for this is scarce and inconclusive, this theoretical risk needs to be considered. In conjunction with the performance of routine pharmacovigilance activities risk minimization measures therefore include exclusion of subjects with untreated parasitic infection and active or recent malignancy.

As with all biologics therapies, anti-drug antibodies (ADA), including neutralizing antibodies (nAb), may develop. Development of ADA to tralokinumab has been rare in the phase 1 and 2

studies conducted thus far (<1% overall). Theoretical risks due to development of ADA include decreased drug efficacy and hypersensitivity reactions (e.g., anaphylaxis or immune complex disease) and observation following administration of tralokinumab is therefore mandated.

Pharmacokinetic modelling suggests that exposure to tralokinumab is slightly higher in adolescents (12-17 years of age) than that in adults; however, considering the overall variability of tralokinumab PK, and the absence of safety findings at doses at or above 300 mg every other week in the phase 2 studies, dose adjustment is not considered to be required for subjects in this age group.

In summary, the efficacy and safety data obtained to date support the continued clinical development of tralokinumab in adult and adolescent subjects with uncontrolled asthma.

A detailed assessment of the risk/benefit of tralokinumab in subjects with asthma is given in the IB.

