### **6.1 Definition of adverse events**

An AE is the development of an undesirable medical condition or the deterioration of a pre-existing medical condition following or during exposure to a pharmaceutical product, whether or not considered causally related to the product. An undesirable medical condition can be symptoms (e.g., nausea, chest pain), signs (e.g., tachycardia, enlarged liver) or the abnormal results of an investigation (e.g., laboratory findings, electrocardiogram). In clinical studies, an AE can include an undesirable medical condition occurring at any time, including run-in or washout periods, even if no study treatment has been administered.

The term AE is used to include both serious and non-serious AEs.

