## **6.8 Study governance and oversight**

### **6.8.1 Independent Adjudication Committee**

Tralokinumab is being developed for the treatment of severe asthma. There is considerable variation in the severity of subjects who seek ER or urgent care, and in the clinical thresholds used to determine the need for hospitalization.

An Independent Adjudication Committee, blinded to subject treatment, will evaluate all ER or urgent care visits, hospitalizations and deaths, to determine whether or not related to asthma. The adjudication committee will also review cardiovascular, cerebrovascular and malignant adverse events occurring after randomization. The committee will include specialists in pulmonology, cardiology, neurology and oncology and will operate in accordance with a dedicated Adjudication Committee Charter/Manual of Operations.

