##### 8.4.4.1 Adverse events

Adverse events experienced by the subjects will be collected throughout the entire study and will be coded by the AstraZeneca designee using the latest version of the Medical Dictionary for Regulatory Activities (MedDRA).

AE data will be categorized according to their onset date into the following study periods:

- AEs occurring during run-in (onset date  $\geq$  Visit 1 and before the first dose of study treatment)
- AEs occurring during treatment (onset date  $\geq$  the first day of study treatment and  $\leq$  the last day of study treatment + 2 weeks)
- AEs occurring during follow-up, consisting of AE with
  - onset date  $>$  the last day of study treatment + 2 weeks and  $\leq$  date of week 72; this is only applicable for subjects that are treated for the entire treatment period
  - onset date  $>$  the last day of study treatment + 2 weeks and  $\leq$  the last day of study treatment + 22 weeks ; this is only applicable for subjects that prematurely discontinued treatment

- AEs occurring post-treatment (onset date > the last day of study treatment + 22 weeks; this is only applicable for subjects that prematurely discontinued treatment)

The timing of AEs will be assigned to the period in which they first occurred. If an AE has a missing onset date, then unless the stop date of the AE indicates otherwise, this will be considered an on treatment event. Similarly, if an AE has a partial onset date, then unless the partial onset date or the stop date indicates otherwise, this will be considered an on treatment AE.

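### As naturally read, the rule for adverse events more than 22 weeks after last dose leaves late deaths, SAEs and malignancies in early discontinuers out of the by-arm summaries

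*Protocol*

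**What the plan says.** Protocol Section 8.4.4.1 sorts adverse events by onset date into run-in, treatment (to last dose plus 2 weeks), follow-up and post-treatment. For subjects who stop early, follow-up closes 22 weeks after the last dose. Later onsets are post-treatment: "onset date > the last day of study treatment + 22 weeks; this is only applicable for subjects that prematurely discontinued treatment".

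Section 8.5.8.1 sets the reporting: "AEs will be summarized separately for the treatment and follow-up periods, as defined in Section 6.3". For the other two periods: "AEs occurring during the run-in period, or occurring post-treatment (as per the definition above) will be listed, but not summarized". A later sentence in the same section adds: "SAEs, OAEs, DAEs, and deaths will also be summarized in separate tables". That sentence names no period. Section 6.1 fixes the scope of the term: "The term AE is used to include both serious and non-serious AEs".

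On follow-up, Section 3.9.1 asks that compliant subjects who stop the investigational product stay for the whole 52 weeks, and gives support of the final efficacy and safety analysis as the reason. Section 4.2 makes AEs and SAEs part of the minimum data at every contact under the two reduced follow-up options. The full option keeps all scheduled procedures.

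**The concern.** The period rule suits ordinary adverse events, where the question is what happens on the drug and shortly after it. It suits deaths, SAEs and malignancies less well, because there the comparison by randomised arm over the whole time observed also matters. Section 1.3 raises a possible role of IL-13 in regulating tumours and says "this theoretical risk needs to be considered". A malignancy may appear long after exposure.

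The group affected is not a random one. Section 3.9.1 stops treatment for, among other reasons, adverse events, anaphylaxis needing epinephrine, asthma-related intubation, malignancy and liver signals. Later serious events in such subjects are among those that would be listed only.

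The rule also sits awkwardly beside the efficacy analysis. Take a subject who stops at Week 4 and is hospitalised for asthma at Week 40. Section 5.1.1 counts that event in the primary endpoint, because exacerbations after stopping treatment are included. It is also an SAE (Section 5.2.2.6), but its onset falls after Week 4 + 22 = Week 26, so on the natural reading it is absent from the SAE summary.

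**Working it through.** **1. Where 22 weeks comes from.** The last scheduled dose is at Week 50 (Section 4.2) and the last follow-up visit at Week 72 (Section 4.3). 72 − 50 = 22 weeks, which is the 2-week on-treatment tail plus 20 weeks. The cut-off reproduces, and it gives early discontinuers the same post-dose window as completers. It also exceeds the 16 weeks that Section 3.8 equates with five half-lives.

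**2. Time left out per subject.** Let w be the week of last dose for a subject followed to Week 52. Time listed but not summarised = max(0, 52 − (w + 22)) = max(0, 30 − w) weeks.

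- w = 0: 30 weeks
- w = 4: 26 weeks
- w = 12: 18 weeks
- w = 20: 10 weeks
- w = 30 or later: 0 weeks

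**3. Total under stated assumptions.** The protocol gives no rate of stopping the investigational product. Its 15% in Section 8.2 is loss to follow-up, which is a different quantity. I assume that 10–15% of 770 subjects stop, that last doses are spread evenly over Weeks 0–48, and that all are followed to Week 52.

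- Share with any time left out: 30/48 = 62.5%.
- Mean per discontinuer: (30²/2)/48 = 9.375 weeks.
- At 10%: 77 subjects, 77 × 9.375/52.18 = 13.8 subject-years.
- At 15%: 115.5 subjects, 115.5 × 9.375/52.18 = 20.8 subject-years.
- Against the planned 710 subject-years: 13.8/710 = 1.9% and 20.8/710 = 2.9%.

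The 710 itself reproduces: 770 × (1 − 0.15/2) = 712.

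**4. Sensitivity.** With last doses even over 52 weeks, the mean is (30²/2)/52 = 8.65 weeks. The totals are then about 6, 13, 19 and 26 subject-years at 5%, 10%, 15% and 20% stopping. In this setting the time left out is (30²/2)/(52²/2) = one third of all time from last dose to Week 52 in discontinuers.

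**5. Boundary.** These figures stop at Week 52, the point to which Sections 3.9.1 and 4.2 keep discontinuers. Section 6.3.1 collects adverse events to Week 72. For a discontinuer who also attended the later visits, the time left out would be 50 − w weeks. I have not counted this.

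**6. Cross-reference.** Section 8.5.8.1 sends the reader to Section 6.3 for the periods. Section 6.3.1 gives only the collection window. The period definitions are in Section 8.4.4.1.

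**The case against.** The strongest defence is that the rule is a consistent exposure-based convention. A reader who sets a Week 4 discontinuer, tabulated to Week 26, beside a completer, tabulated to Week 72, might infer that the cut-off is arbitrary or favours one group. It does not: both are tabulated to last dose plus 22 weeks. Section 8.5.8.1 also plans rates per subject-year at risk, which allow for unequal observation time. This part of the defence stands, and it is why the period tables should be kept.

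A reader might also infer that the late events appear in no safety table at all. The text is less firm than that. The sentence on separate SAE and death tables carries no period limit, so a looser reading would include them. Separate listings of subjects with SAEs and deaths are promised, and an SAP that is not at hand could add an all-period table. Exclusion is still the more natural reading, since the general rule stands in the same section. That a death table can be read two ways is itself a reason to settle the wording.

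A third inference would be that adjudicated cases drop out of the summary they were adjudicated for. Section 6.8.1 says "The adjudication committee will also review cardiovascular, cerebrovascular and malignant adverse events occurring after randomization" with no end date, but Section 8.5.8.1 specifies no summary of adjudicated events, so nothing can be missing from it.

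Finally, the quantity is small. It requires an early stop, continued contact and an onset more than 22 weeks after dosing. An on-study table has its own asymmetry, because the earliest stoppers would have up to about 52 weeks of post-dose observation against 22 for completers. Both points stand and limit the weight of the concern.

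**Conclusion.** The concern holds in a limited form. The exposure-based window is sound for ordinary adverse events. As naturally read, it also removes deaths, SAEs and malignancies arising more than 22 weeks after last dose in early discontinuers from the by-arm summaries. That does not fit the stated reason for keeping these subjects to Week 52.

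Up to Week 52, the 14–21 subject-years are an upper bound for the assumed stopping rates, because they require complete retention. The documents give no event rate, so they do not support a claim that the omitted cases would change the death or malignancy comparison. The events are collected and listed, not lost. This is a worthwhile, inexpensive correction to the reporting plan, not a flaw that undermines the safety objective.

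**What to change.** In Section 8.5.8.1:

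- Keep the treatment-period and follow-up-period tables as they are.
- Add one supplementary on-study summary by treatment group of deaths, SAEs and malignancies, with adjudicated cardiovascular and cerebrovascular events if these are tabulated. It should run from first dose to the end of each subject's participation, whatever the time since last dose, with matching subject-years.
- State whether the separate SAE and death tables include post-treatment events, or refer from them to the new table.
- Correct the reference for the period definitions from Section 6.3 to Section 8.4.4.1.

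The cost is one extra table set from data already collected, with no new visits or procedures. The downside is that late off-drug events dilute attribution and post-dose observation becomes unequal between early stoppers and completers. The retained period tables and the person-time rates address both.

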## 8.2 Sample size estimate

The total study sample of 770 subject (385 subjects per group) are considered sufficient to show a reduction in annualised asthma exacerbation rate for tralokinumab, versus placebo in the overall study population.

Sample size calculations in terms of number of subject years needed is based on an assumed annual exacerbation rate in the placebo group of 0.8, and shape parameter of 0.95 (over-dispersion) in both the all-subject and biomarker positive population. The calculations are made for a 1% significance level for all subjects and a 4% significance level for the biomarker positive population. The methodology used described in [Keene et al 2007](#).

Assuming a uniform loss to follow-up of 15% during the study, 770 randomized subjects are expected to provide approximately 355 subject years at risk per treatment group. This is expected to provide at least 90% power for showing superiority with effects down to 37% asthma exacerbation rate reduction in the all-subject population.

The proportion of subjects in the all-subject population falling within the biomarker positive subpopulation will depend on the biomarker positive criteria to be defined in the SAP before un-blinding of this study. Based on results from study D2210C00007, the testing strategy for this study has been revised to use a 5% significance level based on the biomarker positive population as the primary population, and it is estimated that approximately 20% to 35% of the studied subjects will fulfil the biomarker positive criteria. Using a 5% significance level for the biomarker positive population as the primary population, a true asthma exacerbation rate reduction of 50% would have a power between 70% and 90% to show superiority.

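### The adverse event rate in Section 8.5.8.1 counts subjects but carries the unit events per 100 subject-years, so the unit is wrong

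*Protocol*

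**What the plan says.** Protocol Section 8.5.8.1 plans several AE summaries and in most places keeps subjects and events apart.

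- The overall table gives the number and percentage of subjects with an AE in each category. It adds event counts: "The total number of AEs in the different AE categories in terms of AE counts will also be presented", with repeat occurrences in the same subject included.
- For the tables by preferred term, "for a subject multiple occurrences of an AE will only be counted once".
- The exposure-adjusted rate is "calculated as (number of subjects reporting AE)/(total time at risk of AE), will also be reported".
- The next sentence gives its unit: "Rates will typically be expressed in terms of events per 100 subject-years".

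The protocol does not say when time at risk ends for a subject who has had the AE. Section 8.4.4.1 sets the on-treatment AE period as first dose to last dose plus 2 weeks. Section 8.5.8 applies the safety summaries to the safety analysis set and to the biomarker positive and negative populations.

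**The concern.** Two adjacent sentences fix a numerator and a unit that do not belong together. A subject with four episodes of an AE adds one to the numerator, yet the unit tells the reader that all four were counted. The section distinguishes subject counts from event counts elsewhere, so *events* cannot safely be taken as shorthand for subjects with an event.

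At stake is how the safety tables are read. A reader who takes the unit at face value would believe recurring AEs to be less frequent than they were. If recurrence differed between arms, the figure could hide part of that difference. The planned event counts do not repair this, because they are not divided by time. The same unit would be repeated for each population in which safety is summarized.

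**Working it through.** The protocol states no AE rate, so there is no figure to reproduce. The check compares the defined ratio with the quantity that the unit names.

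**Identity.** Let n be the subjects with at least one occurrence, E all occurrences, T total time on study, and T1 total time with each subject stopped at the first occurrence.

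- The unit names E/T.
- Reading (a), full time at risk: the plan reports n/T = (E/T) ÷ (E/n). Since E ≥ n, this is below the event rate whenever any subject has the AE more than once.
- Reading (b), time to first occurrence: the plan reports n/T1. Here T1 ≤ T, so no general ordering against E/T follows and a model is needed.

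**Inputs.** One year per subject: the last dose is at Week 50, and 50 + 2 = 52 weeks under Section 8.4.4.1. The event rate λ per subject-year and the between-subject dispersion k are assumptions, since the protocol gives neither for AEs. The value k = 0.95 is the shape parameter that Section 8.2 uses for exacerbations and serves here only as one illustrative point. Section 8.2 also says "770 randomized subjects are expected to provide approximately 355 subject years at risk per treatment group", which agrees with 385 × (1 − 0.15/2) = 356. That is efficacy follow-up, which continues after treatment is stopped, so it is not used as the AE denominator.

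**Formulas.** The probability of no occurrence by time t is S(t) = exp(−λt) under Poisson, or (1 + kλt)^(−1/k) under gamma-Poisson. Reading (a) reports 1 − S(1). Reading (b) reports [1 − S(1)] ÷ ∫S(t)dt over 0 to 1.

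**Worked cases at λ = 1 (100 events per 100 subject-years).**

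- (a) Poisson: 1 − exp(−1) = 0.632, reported as 63.2.
- (b) Poisson: the integral is also 0.632, so 0.632/0.632 = 1, reported as 100. There is no understatement.
- (b) k = 0.5: 1 − 1.5^(−2) = 0.556, the integral is 2 × (1 − 1/1.5) = 0.667, and 0.556/0.667 gives 83.3.

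**Results, all per 100 subject-years.**

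| Assumed event rate | (a) Poisson | (a) k = 0.95 | (b) Poisson | (b) k = 0.5 | (b) k = 0.95 | (b) k = 2 |
|---|---|---|---|---|---|---|
| 5 | 4.9 | 4.8 | 5.0 | 4.9 | 4.9 | 4.8 |
| 20 | 18.1 | 16.7 | 20.0 | 19.1 | 18.4 | 16.9 |
| 50 | 39.3 | 33.6 | 50.0 | 45.0 | 41.5 | 35.4 |
| 100 | 63.2 | 50.5 | 100.0 | 83.3 | 73.1 | 57.7 |
| 200 | 86.5 | 67.4 | 200.0 | 150.0 | 123.7 | 89.4 |

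Under (a) with Poisson events the shortfall is about 2% at 5, 21% at 50 and 37% at 100. Under (b) it is zero when all subjects share one constant rate, and it grows with the spread between subjects. In the bottom row it runs from 25% (150.0 against 200) to 55% (89.4 against 200).

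**The case against.** The strongest reply is that nothing is calculated wrongly. Subjects with the AE over time at risk is a standard incidence rate, the formula is stated openly, and it does not claim to count recurrences. That stands: the fault lies in the unit.

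The second reply is that time at risk may be meant to stop at the first occurrence. Each affected subject then contributes exactly one (first) event, and the unit is loose but intelligible. This softens the conflict without removing it. The protocol does not fix that reading, it calls the quantity a rate of AEs, and the figure still falls below the event rate when subjects differ in their rates.

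Third, recurrence is visible in the planned AE counts. That is partly so, but those counts are by category and have no time denominator.

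A reader might be tempted to go further, and the documents do not support it:

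- That the shortfall always equals the mean number of events per affected subject. This holds only under reading (a), and the protocol gives no recurrence figures from which to put a number on it.
- That this is a headline safety figure. Section 8.5.8.1 presents the rate as an addition to the subject and count summaries.
- That the error would pass into a pooled AE analysis with the parallel study. The protocol describes no such analysis.
- That one arm would be favoured. No difference in recurrence between arms is stated or expected.

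**Conclusion.** The point holds as a labelling inconsistency within Section 8.5.8.1. The unit does not match the defined ratio, and a reader who trusts the unit will take the event rate of recurring AEs to be lower than it is. The direction is certain if time at risk is full time. If time stops at the first occurrence, it depends on subjects differing in their rates, and it need not hold where the AE rate falls over time.

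The sizes shown rest on assumed AE rates and dispersion over one year and are not predictions for this trial. For AEs that hardly recur the discrepancy is negligible: at 5 per 100 subject-years it is at most 0.2 in the table. Severity is minor. Safety is analyzed descriptively, and no hypothesis test, sample size or decision rule uses this rate.

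**What to change.** Label the existing ratio *subjects with the AE per 100 subject-years at risk*, and make the definition of time at risk match it, for example ending at the subject's first occurrence of that AE. If an event rate is also wanted, divide the AE counts already planned in the same section by total subject-years, and reserve *events per 100 subject-years* for that figure.

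The cost is one reworded sentence, a table label and, optionally, one extra column. No new data are needed and no other analysis changes.
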